#### 8.10 Interim Analysis

An interim sample size review will be performed after in total  $n_1 = 120$  evaluable subjects (40 subjects per treatment group) have primary endpoint data, i.e., MDS-UPDRS part II+III at Month 2. Evaluable subjects are defined as randomized and having received at least one dose of the study drug. The aim of the interim sample size review is to reassess the size of the estimated mean and SD of the primary effectiveness variable (MDS-UPDRS part II+III). The sample size will be adjusted accordingly (see following section).

No interim analyses are planned for the purpose of stopping the study early for futility.

#### 8.10.1 Re-estimation of Sample Size

The initial sample size estimation provides statistical power to demonstrate effectiveness among subjects treated with buntanetap. A potential sample size adjustment is to assure that this trial will have the intended precision. The decision of sample size adjustment will be made based upon the estimates of MDS-UPDRS part II+III at baseline and after two months of treatment calculated for the first 120 evaluable subjects with primary endpoint data. Sample size will not be decreased regardless of the results of this evaluation. To warrant the originally intended >90% power of the study at the 0.025 alpha level (2-sided), the evaluable sample size may be increased from  $n_2 = 360$  (120 per treatment group) to a maximum of  $n_{max}$ =540 (180 per treatment group). Additional subjects will be enrolled to account for screen failures and drop-outs. The sample size re-estimation will be evaluated for the efficacy endpoint based on the observed interim mean and SD of treatment difference of the MDS-UPDRS part II+III score.

The sample size re-estimation method is based on evaluation of conditional power in relationship to pre-specified decision rules defined by ranges of attainable conditional power values. Only an increase in sample size is possible under this approach when observed conditional power falls within the 'promising zone' as described below (Mehta and Pocock 2011).

The conditional power at the interim analysis is defined by equation (6) from Mehta and Pocock (2011).

The targeted conditional power at the first interim review is 90%, however we pre-specify a range of conditional power values below 90% that would deem our interim results promising and warrant sample size re-estimation. Table 1 provides cut-off values from Mehta and Pocock (2011) for the lower bound of the promising zone,  $CP_{min}$ , under some typical two-stage adaptive designs.  $CP_{min}$  is 0.42 (42%) for the parameter choices ( $n_{max}/n_2 = 1.5$ ,  $n_1/n_2 = 0.33$ ) in this study.

Table 1. C	Pmin cut-of	f values for	some typical	two-stage	adaptive c	designs v	with no ear	ly stopping	either
for efficac	y or futility			_	-	-			

Sample size ratios		CP min values for targeted conditional power	
Maximum allowed	At interim look	80 per cent	90 per cent
(n max / n 2 )	(n 1 / n 2 )	-	
1.5	0.25	0.42	0.42
1.5	0.5	0.41	0.41
1.5	0.75	0.38	0.38
2	0.25	0.37	0.37
2	0.5	0.36	0.36
2	0.75	0.33	0.33
3	0.25	0.32	0.32

CONFIDENTIAL

Version 2.1, 11 January 2024

3	0.5	0.31	0.31
3	0.75	0.30	0.27
∞	0.25	0.32	0.28
∞	0.5	0.31	0.27
∞	0.75	0.30	0.25

**CP: Conditional Power** 

Table 2 summarizes the sample size re-estimation decision based on the conditional power observed at interim analysis. The sample size is re-estimated when the interim conditional power falls within the promising zone of 0.42 to 0.90 (42% to 90%).

Conditional power	Decision
Less than 42%	"Unfavorable zone" – No change to sample size
42% to 90%	"Promising zone" – Increase sample size
At least 90%	"Favorable zone" – No change to sample size

The re-estimated cumulative final sample size ( $n_{2*}$ ) is computed using equations (7-9) from Mehta and Pocock (2011) and will be increased by a factor based on a re-assessed attrition rate as per the initial sample size calculation.

#### 8.10.2 Clarifications Based on Food and Drug Administration (FDA)'s Feedback

The interim analysis for sample size re-estimation has been completed in March 2023. Based on the interim analysis results and sample size re-estimation decision rules, the results of the interim analysis suggested to increase the sample size to 180 randomized subjects per arm. As of June 9, 2023, the study has completed enrollment with a total sample size of 522 (174 per arm) subjects.

The original evaluable sample size was 120 per arm, and a 20% drop out rate was assumed, which rendered to a sample size of 150 randomized subjects per arm (120/0.8=150). Based on the blinded data review, we noticed a low dropout rate of approximately 6%. With this dropout rate, 180 per arm randomized subjects will lead to 170 (180\*0.94) evaluable subjects per arm, which is around 42% increase from originally calculated sample size of 120 per arm (170/120=1.42). The sample size increased was considered reasonably small (42%) based on the Metha and Pocock (2011) paper that the overall Type I error rate will not be inflated.

The sample size re-estimation for our 3-arm study was handled by the worst-case scenario rules in Table 3 below. The sample size re-estimation method evaluates the conditional power in relationship to a pre-specified decision rule defined by ranges of attainable conditional power values. Only an increase in sample size was possible under this approach if observed conditional power was within the Promising Zone.

Outcome	Worst-case Scenario Approach
Both doses Unfavorable	Study proceeds with originally planned sample size
One dose Unfavorable	Study proceeds with sample size re-estimation increase
One dose Promising	suggested by one dose comparison in Promising Zone
One dose Unfavorable	Study proceeds with originally planned cample size
One dose Favorable	Study proceeds with originally planned sample size
	Study proceeds with larger of the sample size re-
Both doses Promising	estimation increases suggested by two dose comparisons
	in Promising Zone
One dose Promising	Study proceeds with sample size re-estimation increase
One dose Favorable	suggested by one dose comparison in Promising Zone
Both doses Favorable	Study proceeds with originally planned sample size

Table 3. Worst-case Scenario Approach to Sample Size Re-estimation for Multiple Dose Comparisons

According to Chen, Yuan and Li (2018), the bias and error rate using the original maximum likelihood estimator (MLE) point estimator and confidence interval should be small and appropriate to use in the final analysis. In addition, the interim analysis was done using the original primary endpoint MDS-UPDRS Part II+III. Based on the Agency's feedback, the original primary endpoint is changed to MDS-Page 24 of 28 UPDRS Part II, and MDS-UPDRS Part II+III is kept as a secondary endpoint. Thus, the results of interim analysis are not relevant to the new primary endpoint. With a sample size of 174 per arm, the study will have 90% power to detect a treatment difference of 3 assuming a common SD of 8, based on a 2-sided t-test with alpha of 0.025.

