6.2. Power and Sample Size Determination

Qualified subjects will be randomized at a 1:1:1 to one of the following three treatment groups: 10 mg, 20 mg QD buntanetap and placebo. A sample size of 360 (120 per treatment group) will have 90% power to detect a treatment difference at a two-sided 0.025 significance level. In the sample size calculation, it was assumed a treatment difference of 2.55 and a common standard deviation of 5.59 based on historical data of MDS-UPDRS Part II+III (details will be provided in the Statistical Analysis Plan (SAP). Approximately 450 subjects will be randomized (approximately 150 per arm) to account for 112 patients calculated from the power analysis plus screen failures and dropout rates.

Based on FDA recommendations, the primary endpoint was changed into MDS-UPDRS Part II after enrollment ended. The current enrolled subject number gives us 90% power to detect a treatment difference of 3 points and a common standard deviation of 8 points of MDS-UPDRS Part II.

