#### 6 Determination of Sample Size

A sample size of up to 450 subjects (1:1:1 randomized to 10 mg, 20 mg buntanetap and placebo respectively) was determined.

Qualified subjects will be randomized at a 1:1:1 to one of the following three treatment groups: buntanetap 10 mg, 20 mg QD and placebo. A sample size of 360 (120 per treatment group) will have 90% power to detect a treatment difference at a two-sided 0.025 significance level. In the sample size calculation, it was assumed a treatment difference of 2.55 and a common standard deviation (SD) of 5.59 based on historical data of MDS-UPDRS Part II+III. Approximately 450 subjects will be randomized (approximately 150 per arm) to account for 120 subjects calculated from the power analysis plus screen failures and dropout rates.

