#### 8.3.1 Level of Significance, Multiple Comparisons and Multiplicity

There are two active treatment groups (10 mg and 20 mg) in the study. Each of the two active treatments will be compared to the control (two hypothesis tests for the primary endpoint). The comparison of each of the two treatment groups against control for the primary endpoint will be performed using the Hochberg step up procedure, where if the largest p-value is <0.05, then the null hypothesis will be rejected for both groups. If the largest p-value is >0.05, then the critical value for the second test will be at two-sided 0.025.

To control for study-wise type 1 error rate, a fixed-sequence hierarchical testing procedure will be applied to adjust for multiplicity arising from multiple secondary endpoints. The hierarchical testing order for the secondary endpoints are:

- 1. Change from baseline to Month 6 in the sum of MDS-UPDRS Part II+III (OFF-state)
- 2. Change from baseline to Month 6 in MDS-UPDRS Part III (OFF-state)
- 3. Change from baseline to Month 6 in MDS-UPDRS Total score (OFF-state)
- 4. Percentage of Responders with "Much Improved" or "Very Much Improved" on PGIC (ON-state)
- 5. Change from baseline to Month 6 on CGIS (OFF-state)

If the primary endpoint of both dose groups are statistically significant, the secondary endpoints for each dose group will be tested in a hierarchical manner at alpha 0.025. If the primary endpoint of a specific dose group is statistically significant, the secondary endpoints for that dose group will be tested in a hierarchical manner at alpha 0.025. If the primary endpoint of both dose groups are not statistically significant, the hypothesis testing for all subsequent endpoints will be considered exploratory. Two flowcharts are also presented in the following.

All other exploratory endpoints are considered supportive and no adjustment for multiplicity will be applied.

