## 8.3.7 Primary Analysis

The primary efficacy endpoint in this clinical trial is the change from baseline to Month 6 in the score for MDS-UPDRS part II (OFF-state) between each of the two regimens of buntanetap and Placebo.

The statistical hypothesis to be tested for primary efficacy is described as:

• Null Hypothesis (H0):

The difference in change in MDS-UPDRS Part II (OFF-state) scores from Baseline to Month 6, between treatment (active vs placebo) regimen = 0.

• Alternative Hypothesis (H1):

The difference in change in MDS-UPDRS Part II (OFF-state) scores from Baseline to Month 6, between treatment (active vs placebo) regimen  $\neq$  0.

The primary endpoint will be analyzed via MMRM. The model will include treatment, timepoint, treatment-by-timepoint interaction as the fixed effects and baseline as the covariate. The variance-covariance matrix will be assumed to be unstructured.

This analysis will be conducted after all subjects have reached Month 6 or early withdrawal, whichever comes first. The primary analysis will be conducted in ITT. The mITT and PPS will be used to support the primary analysis.

Descriptive statistics per visit and change from baseline for each visit will be provided.

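### The 90% power claimed for the Part II primary endpoint counts all 174 enrolled per arm; at the reported 6% dropout the stated t-test gives about 87%, and the inputs (difference 3, SD 8) have no source

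*SAP*

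**What the plan says.** The primary endpoint became Part II after enrollment had ended. Two statements give its power. SAP 8.10.2: "With a sample size of 174 per arm, the study will have 90% power to detect a treatment difference of 3", with a common SD of 8 and a two-sided t-test at alpha 0.025. Protocol 6.2: "The current enrolled subject number gives us 90% power to detect a treatment difference of 3 points", again with an SD of 8.

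SAP 8.10.2 makes clear what 174 is: "the study has completed enrollment with a total sample size of 522 (174 per arm) subjects". It also reports dropout from a blinded data review, "we noticed a low dropout rate of approximately 6"%, and uses dropout to move between randomized and evaluable numbers: 120/0.8 = 150 for the original design, and 180*0.94 for the increased one ("With this dropout rate, 180 per arm randomized subjects will lead to 170" evaluable per arm).

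SAP section 6 still carries only the earlier calculation, in which "it was assumed a treatment difference of 2.55 and a common standard deviation (SD) of 5.59 based on historical data of MDS-UPDRS Part II+III". Unlike 3 and 8, those inputs have a stated origin.

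On the analysis itself, SAP 8.3.7 says "The primary analysis will be conducted in ITT", by a mixed model for repeated measures with the baseline score as covariate. SAP 8.3.1 tests the two doses by Hochberg: "If the largest p-value is >0.05, then the critical value for the second test will be at two-sided 0.025". The 0.025 in the power statement is therefore the stricter of the two Hochberg levels.

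**The concern.** The number in the power claim is a count of people enrolled. For the other two sample sizes in SAP 8.10.2 the plan treats the evaluable number, net of dropouts, as the one that matters. That step is missing for 174, the only sample size behind the power of the endpoint now in force.

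The inputs are a second difficulty. Part II (range 0 to 52) is one component of Part II+III (range 0 to 184), yet it is given a larger effect (3 against 2.55) and a larger SD (8 against 5.59) than the sum. Neither document says where 3 and 8 come from or how they fit with the earlier pair.

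The stake is how the trial is read. A null or borderline result on Part II will be interpreted against this power figure, and a reader cannot tell from the documents whether it is sound.

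**Working it through.** **Inputs.** Difference 3, SD 8, two-sided alpha 0.025, two-sample t-test, 174 enrolled per arm and dropout of about 6%, all from SAP 8.10.2. The Part II+III pair, 2.55 and 5.59, is from SAP section 6.

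**Formula.** With n per arm, difference d and SD s, the noncentrality is d / (s·√(2/n)) on 2n − 2 degrees of freedom. Power is the probability that a noncentral t variable exceeds the two-sided 0.025 critical value, about 2.25 here, in absolute value.

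**1. Reproduce the stated figure.** At n = 174 the noncentrality is 3 / (8·√(2/174)) = 3.50. Power is 89.3% (89.6% by the normal approximation). The stated 90% is therefore reproduced with rounding, provided every enrolled subject counts. As a check on the method, the earlier calculation (2.55, 5.59, n = 120) gives 89.9%, matching its stated 90%.

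**2. Apply the plan's own dropout step.** 174 × 0.94 = 163.6, about 164 evaluable per arm.

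| n per arm | Power, d = 3, SD = 8 |
|---|---|
| 163 | 87.1% |
| 164 | 87.3% |
| 170 | 88.6% |
| 174 | 89.3% |
| 177 | 89.9% |
| 178 | 90.0% |

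90% needs 178 evaluable per arm. At 164 per arm and SD 8, the difference detectable with 90% power is 3.12 points (3.03 at 174).

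**3. Sensitivity to the SD** (d = 3, n = 164; every SD except 8 is an assumption).

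| SD | Power |
|---|---|
| 7 | 94.8% |
| 7.5 | 91.4% |
| 8 | 87.3% |
| 8.5 | 82.7% |
| 9 | 77.8% |

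The largest SD that still gives 90% is 7.68.

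**4. Do the two pairs of inputs fit together?** If both described the same patients and time point, the Part III effect would be 2.55 − 3 = −0.45. Let s3 be the SD of Part III change and r its correlation with Part II change. Then 5.59² = 8² + s3² + 2·r·8·s3, so r = (5.59² − 64 − s3²) / (16·s3). The least negative value is −0.715, at s3 = 5.72. That is possible but hard to reconcile for two motor subscales. It does not show that power is too low. The standardised effect is smaller under the new pair (3/8 = 0.375) than under the old (2.55/5.59 = 0.456), and using 2.55 and 5.59 at 164 per arm gives 97.0%.

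**5. Power under the planned Hochberg test.** A simulation of 1,000,000 trials (shared placebo arm, pooled variance, SD 8, 164 per arm) gives:
- both doses with a 3-point effect: 91.5% for each dose, 96.0% for at least one;
- only one dose effective: 87.8% for that dose.

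**6. Baseline adjustment.** A covariate with baseline-change correlation ρ multiplies the SD by √(1 − ρ²). At 164 per arm, 90% is restored at ρ = 0.28. The documents give no value for ρ.

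**The case against.** The best case for the plan has four parts.

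- **The arithmetic is right for the number named.** 89.3% rounds to about 90%, and Protocol 6.2 says openly that it uses the enrolled number. This stands: the fault is an omitted step, not a miscalculation.
- **Evaluable is also defined more loosely.** The interim analysis sections (Protocol 6.10, SAP 8.10) count anyone randomized who has taken study drug, so a treated dropout would stay in. That definition belongs to the interim review. SAP 8.10.2 nets dropouts out of its evaluable numbers just before it makes the power claim.
- **The 164 completers are not the analysis population.** The ITT mixed model keeps the earlier visits of dropouts and adjusts for baseline, and subjects who leave after five months still have the end-of-trial visit. The 6% is also approximate and not a final rate. All of this stands, so the loss is an upper bound. But the documents base the 90% on a t-test and give no correlations from which a credit could be worked out.
- **Hochberg gives more power than a fixed 0.025 test.** It does when both doses work. When only one works, per-dose power stays near 88%.

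It can also be said that the −0.715 correlation requires both SDs to hold in one population, which the documents do not claim, and that the new inputs are the more cautious pair. Both points are fair; the mismatch is a reason to ask for a source, not evidence of low power. Finally, enrollment is closed, so no decision about numbers turns on this.

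**Conclusion.** The point holds. On its own stated basis, and with the plan's own dropout convention, power for Part II is about 87%, not 90%: about 2 points below the reproduced 89.3% and about 3 below the stated figure. This rests on 6% dropout, a difference of 3, an SD of 8 and a t-test on completers. It is a modest overstatement, and the planned analysis may remove it.

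The missing source for 3 and 8 has more bearing on how far the figure can be trusted: a change of one point in the SD in either direction moves power by 7 to 10 points, several times the effect of the dropout step. Nothing here shows that the trial is too small, and type I error control is not affected.

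**What to change.** In Protocol 6.2 and SAP sections 6 and 8.10.2:

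1. Restate power for Part II as about 87% at about 164 evaluable per arm, or give the difference detectable at 90% power, about 3.1 points at SD 8.
2. Say that this is a two-sample t-test approximation at 0.025, while the planned test is Hochberg on an ITT mixed model.
3. Give the source of the difference of 3 and the SD of 8, or reconcile them with 2.55 and 5.59. A blinded pooled SD of Part II change would serve if it can be obtained; Protocol 6.10 already foresees blinded access to pooled MDS-UPDRS data.

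The cost is a text change in two documents and at most one blinded SD calculation. The stated power becomes slightly less favourable. Enrollment, the analysis and type I error control do not change.

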#### 8.11 Data Monitoring

An independent DSMB (IDMB) will be convened to review the safety information from the study on an ongoing basis. The IDMB, will identify the study-specific data parameters and format of the information to be reported, as well as the timing of reports based on the enrollment status of the study. The IDMB will initially be provided with data blinded to treatment status, but they may request unblinded data if there is a safety concern.

Additionally, the IDMB will be informed of the occurrence of any SAEs probably related to the drug within 7 days of being reported to the Coordinating Center. The IDMB may at any time request additional information from the Coordinating Center.

The IDMB will consist of at least one statistician and two physicians with experience of IDMBs and clinical trials.

The data to be considered by the IDMB, the process for quality control of reports and data, and the documentation of decisions were described in detail in the mutually agreed IDMB charter prior to the study start. The primary responsibility of the IDMB will be to protect the safety of the study subjects.

Based on the review of safety data, the IDMB will make recommendations regarding the conduct of the study. These may include amending safety monitoring procedures, modifying the protocol or consent, terminating the study, or continuing the study as designed. Using the Safety Review Process (review of lab data, vitals, and adverse events) and the IDMB, there is substantial oversight and case review to alert the investigators, in a timely manner, to any safety issues that may arise. Further details will be provided in the IDMB charter.

#### 8.12 Reporting Conventions

Any p-values  $\geq 0.001$  will be reported to three (3) decimal places; p-values <0.001 will be reported as <0.001. PK parameters will be reported to two decimal places. The mean and median will be displayed to one decimal place greater than the original value and the measure of variability (e.g., SD) will be displayed to two decimal places greater than the original value.

# APPENDIX 1: SCHEDULE OF EVENTS

Study Period	Screening/Baseline Up to 42 Days			Double-Blin	Unscheduled Visit h (USV)	Early Discontinuation Visit				
Visit Timing	Day -42 to 0		1 month ± 7 days	2 months ± 7 days	3 months ± 7 days	4.5 months ± 7 days	1-3 days prior to end of trial visit	6 months ± 7 days (end of trial visit) J		
Procedure	Screening I (up to 42 days before Day 0)	Base line J (Day 0)	Clinic Visit	Clinic Visit	Clinic Visit	Phone	Phone	Clinic Visit	Clinic Visit	Clinic Visit
Informed consent	X									
Inclusion and exclusion criteria	x	X								
Demography information	x									
Full physical examination and neurological examination	x	x	x	x	x			x	x	X
Height, Weight, BMI	x									
Medical and psychiatric history (includes substance use)	x									
Urine pregnancy test (WOCBP only)	x	x	X	x	x			x	X	X
Hoehn & Yahr Stage	x									

ANNOVIS BIO, INC.

ANVS-22001

CONFIDENTIAL

Statistical Analysis Plan

Study Period	Screening/Baseline Up to 42 Days			Double-Blir	Unscheduled Visit h (USV)	Early Discontinuation Visit				
Visit Timing	Day -42 to 0		1 month ± 7 days	2 months ± 7 days	3 months ± 7 days	4.5 months ± 7 days	1-3 days prior to end of trial visit	6 months ± 7 days (end of trial visit) J		
Procedure	Screening I (up to 42 days before Day 0)	Base line J (Day 0)	Clinic Visit	Clinic Visit	Clinic Visit	Phone	Phone	Clinic Visit	Clinic Visit	Clinic Visit
MMSE	X	Х						X		
PGIC			X	X	X			X		
CGIS		Х	Х	Х	X			X		
WAIS-IV		Х		X				X		
MDS-UPDRS		Х	Х	X	X			X		
C-SSRS	X	Х	Х	X	X	X	X	X	X	Х
Clinical Laboratory safety tests d&g	x	x	x	x	x			x	x	х
12-lead ECG	X	Х	Х	X	X			X	X	X
Vital signs a	X	X	X	x	x			X	X	x
Randomization		Х								
Study intervention dispensed		x	x	x	x			X f		
Study intervention compliance review			x	x	x	x	x	x		x
AE/SAE review	X	Х	X	X	X	X	Х	X	X	X
Concomitant medication review	X	X	X	x	x	x	x	X	x	x

Study Period	Screening/Baseline Up to 42 Days		Double-Blind Trial Treatment Period 6 Months e						Unscheduled Visit h (USV)	Early Discontinuation Visit
Visit Timing	Day -42 to 0		1 month ± 7 days	2 months ± 7 days	3 months ± 7 days	4.5 months ± 7 days	1-3 days prior to end of trial visit	6 months ± 7 days (end of trial visit) J		
Procedure	Screening I (up to 42 days before Day 0)	Base line J (Day 0)	Clinic Visit	Clinic Visit	Clinic Visit	Phone	Phone	Clinic Visit	Clinic Visit	Clinic Visit
PK sampling c		X						X		
Sampling for blood biomarkers		X						X		
24-hour phone follow-up b		X	x	x	x			x	X	x

a=Vital signs include sitting blood pressure, pulse, temperature, respiration rate.

b=Phone follow-up should occur approximately 24 hours after baseline, each clinic visit and after discharge from the end of trial or early discontinuation visits.

c=Sampling Times: 0 (pre-dosing) and 1.5hrs after dosing, except for 16-people per group who will go through 10hr sampling timepoints at 0, 1hr, 1.5hr, 2hr, 3hr, 4hr,5hr, 6hr, 7hr, 8hr, 9hr, and 10hr (±10 mins for all collection timepoints). Intense PK subgroup is only in the US.

d=Safety labs at all clinic visits should be taken fasted.

e=Subjects who drop out after the initial 5 months of study treatment will complete the full End of Trial visit. Subjects who dropped out prior to the initial 5 months of study treatment will complete the Early Discontinuation Visit assessments.

f=The study intervention dispensing on the end of trial visit is only for the one pill given on that day.

g=Blood and urine samples will be obtained for clinical safety lab assessments as described in the Laboratory Manual.

h= Investigator will determine the extra assessment if any is needed.

i= With investigator's permission, lab re-testing is allowed within a month.

j= For the intense PK subgroup participants, baseline visit and end-of-trial visit can be done in 2 days.
